### 5.3.2 90-day follow-up for Quality of Life assessment

Sites may choose to participate in a long-term outcomes substudy exploring the effects of ascorbic acid, hydrocortisone, and thiamine vs. placebo on quality of life following sepsis. If a site chooses to participate, a trained research assistant/investigator at the site (who is blinded to treatment arm) will contact all participants who were alive at 30-days, and perform the SF-36 at day 90 following enrollment. The SF-36 is a 36-Item Short-Form Health Survey (SF-36), a validated survey of general quality of life in adults, can be administered in person or over the telephone by research personnel. It measures eight different dimensions: physical functioning, bodily pain, role limitations due to physical health problems, role limitations due to personal or emotional problems, emotional well-being, social functioning, energy/fatigue, and general health perceptions, as well as one question asking about perceived changes in health. The telephone version of the 36-Item Short-Form Health Survey has been validated and used in sepsis.

## 5.4 Safety

### 5.4.1 Definitions

The following definitions will be used:

**Adverse event:** any untoward medical occurrence in a participant to whom a medicinal product is administered and which does not necessarily have a causal relationship with this treatment

**Serious adverse event:** any untoward medical occurrence that at any dose requires inpatient hospitalization or prolongation of existing hospitalization, results in persistent or significant disability or incapacity, results in a congenital anomaly or birth defect, is life-threatening, or results in death

**Unexpected serious adverse event:** a serious adverse reaction, the nature, severity or outcome of which is not consistent with the reference safety information

### 5.4.2 Specific adverse event data collection

To assess specific and potentially serious adverse events that may be related to the combination of the study medications, we will collect data on the following:

Serious Adverse Event	Definition
Hyperglycemia	Serum glucose >300mg/dl in the first 120-hours after enrollment
Hypernatremia	Serum sodium (> 150 mmol/L) occurring in the first 120-hours after enrollment
New Infection	As determined by the site principal investigator at each site. Should be a new organism or site of infection and believed to be unrelated to the initial presenting infectious source. Many will have the initiation of new antibiotics or a change in antibiotics.
Catheter-site	
Lung	
Gastrointestinal	
Urinary tract	
Other	
Serious allergic reaction	Anaphylaxis or other allergic reaction requiring systemic corticosteroids. Allergic reaction should be related (or suspected to be related) to the study medication
Renal calculus	Development of a renal calculus between enrollment and 30-day follow-up (based on question asked during follow-up phone call).

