##### Specimen Collection Time Points

1. T1=0 hrs (just before study drug administration)
2. T2=24 hrs (+/- 2 hrs)
3. T3=72 hrs (+/- 2 hrs)
4. T4=120hrs (+/- 12hrs)

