##### *4.5.2 Specimen samples*

At the T1, T2, T3, and T4 time points, blood will be sent for complete blood count (including hemoglobin, white blood cell count, platelet count), a serum chemistry (including sodium, potassium, chloride, bicarbonate, blood urea nitrogen, creatinine, glucose, aspartate transaminase, alanine transaminase, and total bilirubin), and a venous blood gas to measure lactate. These tests will be performed by the clinical laboratory at each site. As many of these laboratory tests are commonly obtained for clinical purposes, these tests do not need to be repeated if a result is available from the clinical care of the participant within 2 hours of the time point (or within 12 hours of the T4 time-point).

In addition to traditional clinical markers, blood will be obtained for future biomarker analysis (including inflammatory biomarkers, markers of endothelial function, and markers of mitochondrial function), and measurement of vitamin C, vitamin B1, and cortisol levels. The total volume of blood that may be drawn for a participant at each time point will not exceed 60mls. Levels of vitamin C, vitamin B1, and cortisol will be measured at time T1 and time T3 only. 20ml of urine will be collected for future biomarker analysis at T1, T2, and T3.

[figure not shown]
If performed as part of standard-of-care, results of urinalysis and urine sediment testing will be collected prior to enrollment.

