### 6.2.3 30-day mortality

Survival until 30 days will be analyzed using survival analysis. Participants lost to follow-up will be censored and the censoring will be assumed non-informative. Results will be presented with Kaplan-Meier curves and the groups compared using the log-rank test. Hazard ratios with 95% confidence intervals will be obtained using Cox's proportional hazards models. The proportional hazards assumption will be verified by visual inspection of the Kaplan-Meier curves and statistically by including a product term (i.e. "interaction") between the treatment group variable and the natural logarithm of time in the model. If the proportional hazards assumption is not met, only the Kaplan-Meier curves and the p-value from the log-rank test will be presented.

Adverse events and other binary outcomes will be presented and analyzed like renal failure.

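### The hyperglycemia and high-sodium events have no baseline condition, so they mix new onset with persistence of a pre-dose abnormality

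*Protocol*

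**What the plan says.** The table in Protocol section 5.4.2 lists events collected because they might be related to the study drugs. Hyperglycemia is "Serum glucose >300mg/dl in the first 120-hours after enrollment". The sodium event is "Serum sodium (> 150 mmol/L) occurring in the first 120-hours after enrollment". SAP section 5.4.2 uses the same thresholds and window.

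Two other rows of the same table do carry an onset condition. For new infection the text is "Should be a new organism or site of infection and believed to be unrelated to the initial presenting infectious source", and renal calculus is "Development of a renal calculus between enrollment and 30-day follow-up".

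A baseline value is available. The first sampling point is "T1=0 hrs (just before study drug administration)", and the panel sent at every time point includes "a serum chemistry (including sodium, potassium, chloride, bicarbonate, blood urea nitrogen, creatinine, glucose" (Protocol section 4.5.2).

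On analysis, section 6.2.3 says: "Adverse events and other binary outcomes will be presented and analyzed like renal failure". Section 6.2.2 gives renal failure a Fisher's exact test with no adjustment. Section 6.2.1 makes tests two-sided at 0.05 in all participants who received a first dose. No exclusion in section 3.3 concerns diabetes, high glucose or high sodium.

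**The concern.** Take a participant who arrives in septic shock with a glucose of 400 mg/dl and is still above 300 mg/dl a few hours after the first dose. Under the rule as written this is an event, in either arm. The abnormality began before any study drug, so its onset says nothing about the drug. Only its duration might.

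Two things are at stake. The first is meaning: a reader or the DSMB will take the count as new metabolic toxicity, when part of it is carried-over illness. The second is sensitivity: if carried-over cases are about equally common in both arms, they add events without adding contrast. Hyperglycemia is one of the risks of hydrocortisone named in Protocol section 8.1.2, and the DSMB works without formal statistical criteria (section 9.2), so it relies on counts that are easy to interpret.

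**Working it through.** **Method check.** The plan states no rate or power for either laboratory event. The nearest stated figure with the same test and sample size is renal failure in section 6.1: 30% vs 55%, 100 per arm, Fisher's exact test, 94% power. Exact enumeration of the two-sided Fisher test at 0.05 gives 93.9%, so the routine reproduces the plan's figure.

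**Inputs.** From the documents: 100 per arm, two-sided 0.05, Fisher's exact test, T1 glucose and sodium measured. Assumed, because the documents are silent:
- new-onset risk r0 = 10% (placebo) and r1 = 25% (active);
- share b already over the threshold at T1, the same in both arms by randomization;
- share s0, s1 of those participants who have a later value over the threshold.

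**Formulas.**
- As written, with n = 100 per arm: p = b·s + (1 − b)·r in each arm. The risk difference is (1 − b)(r1 − r0) + b(s1 − s0).
- New onset only: n = 100(1 − b) per arm, risks r0 and r1, so the risk difference is 15 points and the risk ratio 2.5 at every b. That part is true by construction.

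**Full persistence in both arms (s0 = s1 = 100%).** Example at b = 10%: placebo 0.10 + 0.90 × 0.10 = 19.0%; active 0.10 + 0.90 × 0.25 = 32.5%; ratio 32.5/19.0 = 1.71.

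| b | As written: placebo vs active | Risk ratio | Power as written | New onset: n per arm | Power, new onset |
|---|---|---|---|---|---|
| 1% | 10.9% vs 25.75% | 2.36 | 73% | 99 | 76% |
| 2% | 11.8% vs 26.5% | 2.25 | 71% | 98 | 75% |
| 5% | 14.5% vs 28.75% | 1.98 | 63% | 95 | 74% |
| 10% | 19.0% vs 32.5% | 1.71 | 53% | 90 | 71% |
| 15% | 23.5% vs 36.25% | 1.54 | 45% | 85 | 68% |
| 20% | 28.0% vs 40.0% | 1.43 | 37% | 80 | 65% |

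**Other persistence assumptions, at b = 10% (new-onset power 71%).**

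| s0, s1 | As written: placebo vs active | Risk difference | Risk ratio | Power as written |
|---|---|---|---|---|
| 60%, 60% | 15.0% vs 28.5% | 13.5 points | 1.90 | 58% |
| 50%, 70% | 14.0% vs 29.5% | 15.5 points | 2.11 | 71% |
| 50%, 80% | 14.0% vs 30.5% | 16.5 points | 2.18 | 76% |

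The formula shows where the direction turns. The risk difference as written is below 15 points only when the gap in persistence, s1 − s0, is smaller than the gap in new-onset risk, r1 − r0. The risk ratio is still below 2.5 in the last two rows, because the persistence ratios (1.4 and 1.6) are below 2.5.

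**Other new-onset rates, full persistence.** With 5% vs 15%: 41% as written vs 56% at b = 5%, and 31% vs 55% at b = 10%. With 2% vs 8%: 28% vs 36% at b = 2%.

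**The case against.** The strongest reply is that dilution is not a given. A participant over the threshold at T1 counts only if a later value is also over it, and a steroid can affect whether glucose stays high. Such participants may then carry signal: with assumed persistence of 50% vs 80% the rule as written has more power than the new-onset rule (76% vs 71%). This stands, and it is why the all-participants comparison should be kept.

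The size is also unknown. At 1% to 2% baseline prevalence the loss is about 2 to 4 points even under full persistence. This stands too.

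Three further points stand in part. Randomization keeps the Fisher test valid when there is no effect, so no false signal arises. Section 5.4.1 does not require causality for an adverse event, so an all-participants count is a legitimate safety summary; it does not, however, answer the new-onset question. Finally, the derivation might be given in the data dictionary or CRF, which are not part of these documents.

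Two stronger readings are tempting. A reader might infer that these two events are the comparison most likely to reveal steroid harm. Section 8.1.2 supports this for hyperglycemia only in that it names it as a risk. It names hyponatremia rather than high sodium, and it also discusses secondary infection, whose definition already requires newness. A reader might also infer a material gap between enrollment and first dose. The Protocol largely ties the two together: section 5.1.1 puts enrollment at time zero, T1 is at 0 hours just before study drug, and section 4.3 treats a consented patient who is not dosed because the vasopressor has stopped as not enrolled.

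**Conclusion.** The definitions lack a baseline condition that other rows of the same table have, and the data needed to supply one are already collected. Followed as written, the rule scores some pre-dose abnormalities as drug-safety events and mixes onset with persistence.

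Attenuation is conditional. It requires a non-trivial share of participants over the threshold at T1 and similar persistence in the two arms. Under the assumed 10% vs 25% risks and full persistence, the power loss is about 4 points at 2% prevalence, 11 at 5% and 18 at 10%. Under sufficiently different persistence there is no loss, although the risk ratio still understates the assumed new-onset effect in the cases shown.

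This is a cheap improvement, not a flaw that invalidates the safety analysis. The case is strongest for glucose. For sodium there is a separate labelling problem: the Protocol calls the event above 150 mmol/L hypernatremia, the current SAP text calls it hyponatremia, and section 8.1.2 names hyponatremia as the risk. A threshold above 150 mmol/L cannot detect low sodium.

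**What to change.** In section 5.4.2 of both documents:
1. Add a new-onset event for each analyte: a first value over the existing threshold after the first dose, within the existing 120-hour window, in participants at or below the threshold at T1. Compare it by arm with the planned Fisher's exact test.
2. Report participants over the threshold at T1 separately by arm, with the number who have a later value over it, so that any prolonging effect remains visible.
3. Keep the all-participants comparison alongside the new-onset one, for the DSMB and the final report.
4. Reconcile the sodium label between the Protocol and the SAP, and with the risk named in section 8.1.2.

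The cost is a short wording change, one derived variable per analyte from chemistry already drawn, and one extra analysis for each event. The new-onset comparison has a slightly smaller denominator, for example 90 rather than 100 per arm at 10% baseline prevalence. No new sampling is needed.

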##### 5.1.2 Key Secondary Outcomes

Incidence of Acute Renal Failure – Renal failure will be defined as the development of Kidney Disease Improving Global Outcomes [KDIGO] Stage 3 acute kidney injury during the index ICU stay after study enrollment.

KDIGO Stage	Serum creatinine criteria	Urine output criteria
1	Increase in serum creatinine of more than or equal to 0.3 mg/dl ( $\geq$ 26.4 $\mu$ mol/l) or increase to more than or equal to 150% to 200% (1.5- to 2-fold) from baseline	Less than 0.5 ml/kg per hour for more than 6 hours
2	Increase in serum creatinine to more than 200% to 300% (> 2- to 3-fold) from baseline	Less than 0.5 ml/kg per hour for more than 12 hours
3	Increase in serum creatinine to more than 300% (> 3-fold) from baseline (or serum creatinine of more than or equal to 4.0 mg/dl [<math>\geq</math> 354 <math>\mu</math>mol/l]) with an acute increase of at least 0.5 mg/dl [44 <math>\mu</math>mol/l])	Less than 0.3 ml/kg per hour for 24 hours or anuria for 12 hours OR New renal replacement therapy (RRT)

**30-Day Mortality** – Mortality at 30-days. This will be assessed by review of the medical records if the participant remains in the hospital or if the participant expired while in the hospital. If the participant was discharged, 30-day mortality will be assessed by contacting the participant by phone or by searching the National Center for Health Statistics (NCHS) National Death Index (NDI) consistent with a recent multicenter phase III trial in sepsis. Phone calls will be made by the research team at each site.

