## 6. SAMPLE SIZE CALCULATION AND STATISTICAL ANALYSIS PLAN

### 6.1 Sample size calculation

The study has been powered to have at least 80% power for the primary outcome and all key secondary outcomes as follows:

**SOFA Score:** Based on preliminary data, we conservatively anticipate a decrease in SOFA score of 6 (standard deviation [SD]: 4) in the treatment group and 4 (SD: 2) in the placebo group. With these estimates, enrollment of **200 participants (100/arm)** at an alpha of 0.05 and using a t-test with unequal variance, the trial will provide > 99% power to detect a statistical significant difference between groups.

**Kidney Injury:** Based on preliminary data from our study of vitamin B1 in septic shock, we anticipate that 30% of participants in the treatment group and 55% in the placebo group will have renal failure which will result in a 94% power for this outcome. This calculation and following calculation were performed using the Fisher's exact test.

**Mortality:** Based on preliminary data, we anticipate that the control group will have a mortality of 40%. We estimate a treatment effect of 50% (risk ratio: 0.50) resulting in a mortality of 20% in the treatment group. With these estimates, 182 participants will lead to 80% power. To further increase

the trial's power and due to potential loss-to-follow-up, we will aim to enroll 200 participants. These estimates are conservative compared to the Marik et al. study which found a treatment effect corresponding to a risk ratio of 0.21 which persisted in adjusted analysis.

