### 6.2.2 SOFA score and renal failure

The change in SOFA score will be calculated and compared between groups using the Wilcoxon Rank Sum test (if the change is not normally distributed) or by a t-test if the change is approximately normally distributed. Fisher's exact tests will be used to compare the incidence of renal failure during the index ICU stay.

If a participant expires prior to the 72-hour time point, SOFA scores will be imputed based on a pre-defined plan as follows. If a participant expires before 24-hours has elapsed, a 20% increase from baseline will be imputed. If a participant expires between 24-hours and 48-hours, a 15% increase from the 24-hour time point will be imputed. If a participant dies between 48-hours and 72-hours, a 20% increase from the 24-hour time point will be imputed. Sensitivity analyses will be performed using various other imputation techniques. Specifically, we will perform 1) a sensitivity analysis in which the worst possible SOFA score (score of 24) is imputed for those participants who expire, 2) a sensitivity analysis in which the last SOFA score for participants who expire will be carried forward, and 3) a sensitivity analysis in which only those patients who survive to 72-hours are included. These sensitivity analyses were chosen to model 'worst-possible' and 'best-possible' scenarios. For the secondary outcome of renal failure, participants who expire during their ICU stay will be assessed to have developed renal failure if they demonstrated any degree of unresolved KDIGO acute kidney injury prior to death. If there was no evidence of acute kidney injury prior to death or if kidney injury had fully resolved, these participants will be assessed as not having developed renal failure.

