## 7. DATA COLLECTION AND MANAGEMENT

### 7.1 Data collection process

Data collection will be the responsibility of the individual site investigators with oversight from the trial coordinating center. Most variables (i.e. demographics, sepsis characteristics and laboratory results) will be obtained prospectively from the electronic medical record. 30-day follow-up regarding safety and mortality end-points will be obtained via telephone call post-discharge (unless the participant remains in the hospital at 30-days). Data will be entered directly into the online database software (see below).

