#### *8.1.2 Potential harms*

##### **Study Drug**

Vitamin C – Ascorbic acid is a water-soluble essential vitamin that is safe even at high doses. Nevertheless, adverse effects related to high-dose ascorbic acid have been described. These adverse effects include diarrhea/abdominal bloating, increased oxalate excretion, iron overload in participants with hemochromatosis, and hemolysis in participants with G6PD deficiency. We exclude participants with known renal failure, known G6PD deficiency, or known hemochromatosis to limit these potential risks. We will additionally exclude participants with known allergy to ascorbic

acid. Ascorbic acid has additionally been used in at least 3 clinical trials in critically-ill populations without major associated adverse effect.

Hydrocortisone – Hydrocortisone is a well-established medication for the treatment of refractory shock in sepsis. Some studies (e.g. CORTICUS) have found an increased incidence of secondary infection in participants with septic shock who receive steroids. This finding has not been replicated in other large trials of corticosteroids for sepsis. Additional hypothetical risks to the administration of hydrocortisone to participants with septic shock (e.g. increased gastro-intestinal bleeding, muscle weakness, and delirium) have not been found in clinical trials of corticosteroids in sepsis. Finally, hydrocortisone may increase the risk of hyperglycemia and hyponatremia.

Hydrocortisone will not be tapered in this study as prior studies have shown benefit with corticosteroids in septic shock without a taper. In addition, a recent large trial of corticosteroids in septic shock (ADRENAL, NEJM 2018) randomized patients to 7-days of corticosteroids or placebo and did not include a taper. In that trial there was no reported difference in rates of recurrent shock.

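### Renal calculus has a phone question as its only named source, so participants who die or are not reached have no stated assessment, and their coding is left open

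*Protocol*

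**What the plan says.** **Definition.** Protocol 5.4.2 lists renal calculus among the specific adverse events and defines it as "Development of a renal calculus between enrollment and 30-day follow-up (based on question asked during follow-up phone call". The SAP carries the same definition.

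**Route.** Section 7.1 states that "30-day follow-up regarding safety and mortality end-points will be obtained via telephone call post-discharge (unless the participant remains in the hospital at 30-days". Section 5.1.2 allows vital status after discharge to be settled without a conversation: "30-day mortality will be assessed by contacting the participant by phone or by searching the National Center for Health Statistics (NCHS) National Death Index".

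**Why the event is collected.** Section 8.1.2 says of vitamin C: "These adverse effects include diarrhea/abdominal bloating, increased oxalate excretion". Section 3.3 excludes people with a known stone in the past year and sets aside stones found incidentally on imaging. So the trial itself treats stones as a risk of interest.

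**Analysis.** Section 6.2.3 states: "Adverse events and other binary outcomes will be presented and analyzed like renal failure". For renal failure, section 6.2.2 says that Fisher's "exact tests will be used to compare the incidence of renal failure during the index ICU stay". It also has a rule for deaths: where there was no kidney injury before death, or it had fully resolved, "these participants will be assessed as not having developed renal failure". Section 6.2.1 puts everyone who received a first dose into every analysis. No corresponding death rule is written for renal calculus.

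**The concern.** The window covers the whole period from enrollment to day 30, yet the named source works only for someone who is alive, discharged, reached, aware of the stone and able to report it. The other events in the same table (glucose, sodium, new infection judged by the site, allergic reaction) can be established by site staff or from the record whether or not the participant survives.

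Three groups fall outside the stated method:

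- participants who die before the call;
- survivors not reached, including those whose status comes from the National Death Index;
- participants still in hospital at day 30, who are exempt from the call but for whom no other method is named.

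A stone imaged or treated during the index admission is well documented, but the stated source can miss it. The trial also expects mortality to differ by arm, so the share that cannot be asked would differ too. At stake is the reliability of one pre-listed safety comparison. The primary and key secondary outcomes are not affected.

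**Working it through.** **1. Inputs.** Section 6.1 says "we anticipate that the control group will have a mortality of 40" percent, and halves it to 20% on treatment. Target enrollment is 100 per arm. Tests are two-sided at 0.05. The documents give no stone rate.

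**2. The plan's own figure.** For 40% versus 20% with 80% power, the normal-approximation size per arm is

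n = [1.96·√(2·0.30·0.70) + 0.8416·√(0.40·0.60 + 0.20·0.80)]² / 0.20² = (1.270 + 0.532)² / 0.04 ≈ 81.2.

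That is 82 per arm, or 164 in total. The continuity correction gives (81.2/4)·[1 + √(1 + 4/(81.2·0.20))]² ≈ 91 per arm, or 182 in total, which is the stated number. Exact enumeration of Fisher's test at 91 per arm gives 80.8% power. The mortality rates used below are therefore the ones that produced the plan's own sample size.

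**3. Who can be asked.** Alive at day 30 per 100: 100·(1 − 0.20) = 80 active and 100·(1 − 0.40) = 60 placebo. Death alone leaves 20 versus 40 unasked. If an assumed further 10% of survivors in each arm are not reached, 72 and 54 remain.

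**4. Conditional effect on the ratio.** Suppose unassessed participants were coded event-free, and stone risk were the same in both arms and the same in people who die as in survivors. The recorded ratio is then (1 − mortality on active)/(1 − mortality on placebo). A non-contact share common to both arms cancels.

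| Mortality, active vs placebo | Recorded ratio when the true ratio is 1 |
|---|---|
| 20% vs 40% (plan) | 0.80/0.60 = 1.33 |
| 20% vs 30% | 0.80/0.70 = 1.14 |
| 30% vs 30% | 1.00 |
| 40% vs 20% (reversed) | 0.60/0.80 = 0.75 |

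If unassessed participants were instead dropped, the ratio under the same assumptions is 1.00. The comparison is then limited to reached survivors, and any stone in a participant who died is still lost.

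**5. If people who die form fewer stones.** Let their risk be k times the survivors' risk, with survivors' risk equal in the two arms. At the plan's mortality the recorded ratio stays at 1.33, and the true ratio is (0.80 + 0.20k)/(0.60 + 0.40k). The distortion is the recorded ratio divided by the true one:

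- k = 1: 1.33/1.00 = 1.33
- k = 0.5: true ratio 0.90/0.80 = 1.125, distortion 1.33/1.125 = 1.19
- k = 0: true ratio 0.80/0.60 = 1.33, distortion 1.00

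**6. Absolute size.** The stone risks below are assumed, equal in both arms, with event-free coding and the plan's mortality.

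| Assumed risk | Recorded per 100, active vs placebo | Fisher false-positive rate |
|---|---|---|
| 1% | 0.8 vs 0.6 | 0.0001 |
| 2% | 1.6 vs 1.2 | 0.0020 |
| 5% | 4 vs 3 | 0.0214 |
| 10% | 8 vs 6 | 0.0495 |

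The gap is 0.2 to 2 recorded events per 100, and the false-positive rate stays at or below 5%.

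**The case against.** A reader might infer that people who die are entered in the comparison as stone-free. The documents do not say so. Section 6.2.1 fixes who is analysed, not how an unanswered item is coded. The instruction to analyse adverse events like renal failure can be read in two ways. It may import only the test, in which case unasked participants could simply be missing. Or it may also import the death rule, which looks at evidence before death and so points to the record. Event-free coding is a natural reading, but it remains an inference.

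A reader might also infer that no stone can be counted without a phone answer. That too goes further than the text. Section 7.1 exempts participants still in hospital at day 30 and says most variables come from the electronic record. Section 15 makes site investigators responsible for adverse drug event data. The case report form and data dictionary are not among the documents, so an inpatient field may exist.

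The 1.33 stacks three conditions: event-free coding, the full planned mortality contrast, and equal stone risk in people who die. The last is strained for someone who dies on day 2. In the planned direction the error would overstate harm; masking at 0.75 needs mortality to run the other way.

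All of this stands, and it limits the size of the point. It does not remove the gap. The definition names one source, that source cannot serve the participants who die or are not reached, and the unassessed share differs by arm whenever mortality differs, however the blanks are coded.

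**Conclusion.** The point holds as a gap in ascertainment and in the stated denominator. The named source leaves participants who die and survivors not reached without an assessment, and no method is given for those still in hospital at day 30. At the plan's mortality rates, death alone makes the unassessed share about 20 versus 40 per 100.

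The documents do not establish that the safety table will be biased by a third. A ratio of 1.33 (0.75 with mortality reversed) is the ceiling at those mortality rates. It assumes event-free coding and that people who die have no higher stone risk than survivors, and it shrinks as their risk falls. The likelier harm is lost events and a table whose denominator cannot be interpreted, rather than a false significant result. The improvement is worth making because the risk is one the trial itself flags and the remedy is cheap.

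**What to change.** - Ascertain renal calculus from the medical record (imaging, passage or treatment) for every dosed participant, from first dose to the earliest of death, discharge or day 30. Record incidental imaging findings separately, in line with the stone exclusion in section 3.3.
- Use the phone question only for the interval between discharge and day 30.
- In section 6.2, state how unassessed participants are handled, and do not silently code them as event-free. Report the number assessed in each arm beside the all-dosed count.

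**Cost.** One case report form item at death, discharge or day 30, a few minutes of chart review per participant, and a sentence or two in the analysis plan. No treatment or visit changes.

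**What it does not solve.** Longer survivors still have more time and more imaging in which a stone can be found. An assessed-only denominator conditions on survival and contact. Both counts should therefore be shown as descriptive.
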